#### Sunitinib dose levels\*

Dose Level	Daily Dose
-3	12.5 mg
-2	25 mg
-1	37.5 mg
0	50 mg

\* dispensed using 12.5mg, 25mg and 50mg capsules as applicable

The major toxic effects of sunitinib which may limit dose are: neutropenia, thrombocytopenia, fatigue, hand-foot syndrome, hypertension, and changes in liver enzymes. The guidelines that follow outline dose adjustments for several of these toxic effects. If a patient experiences several adverse events and there are conflicting recommendations, please use the recommended dose adjustment that reduces the dose to the lowest level.

For all dose modifications, please note:

- Cycle length of 6 weeks should be maintained even if doses are missed during the 4 weeks of planned treatment (i.e. treatment interruptions should not re-set the cycle timing such that the next cycle starts earlier and missed doses should not be 'made up' in the observation period during weeks 5 and 6). However, the cycle length may be increased in the event that a new cycle of treatment is delayed.
- Supportive care recommendations for sunitinib-related effects can be found in section 8.1.3.
- Patients requiring more than three dose reductions will be removed from protocol therapy.
- Patients who do not recover from toxic effects as required within 3 weeks will be removed from protocol therapy.
- No dose escalations are permitted after reductions for confirmed toxicity (except for the circumstance as described for QTc prolongation in section 8.3).

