### 8.3.4 Other Non-Hematologic Adverse Events

Event	AE Grade	Dose modification
	or	
	Observation	
Fever, chills, flu-like	Grades 1-4	Maintain dose
symptoms		
	Grades 1 and 2	Maintain dose
Fatigue (lethargy,	Grade 3 *	Hold sunitinib until $\leq$ grade 2, then reduce 1 dose
		level and resume treatment
malaise, asthenia)	Grade 4	Hold sunitinib until $\leq$ grade 2, then reduce 1 dose
		level and resume treatment
	>450 but	Review patient's concomitant medications for
	< 550 msec	QT interval-prolonging agents. Correct any
		electrolyte abnormalities.
		Continue sunitinib at current dose level.

\* If neutrophil and/or platelet counts have not recovered to baseline or better within 3 weeks of dose interruption, the patient is withdrawn from the study \* Recurrent grade 3 events require dose reduction.

QTc Prolongation	≥ 550 msec	Stop sunitinib and any other QT-interval prolonging agents immediately. Correct any electrolyte abnormalities, then  1. If there is a plausible explanation for AE other than sunitinib treatment, resume sunitinib at current dose level.  2. If sunitinib may have contributed to the AE:  Reduce 2 dose levels and restart sunitinib.  If QTc remains <500 msec after 14 days at reduced dose, increase one dose level and continue sunitinib.  If QTc remains <500 msec after 14 days, original
		dose of sunitinib may be resumed.
	Grades 1 and 2	Maintain dose
	Grade 3 *	Hold sunitinib until $\leq$ grade 1, then resume
Hand-foot syndrome		treatment at same dose or reduce 1 dose level
	Grade 4	Hold sunitinib until $\leq$ grade 1, then reduce 1 dose
		level or discontinue treatment
	Grades 1-2	Maintain dose *
AST and/or ALT	Grades 3-4	Sunitinib held until ≤grade 2,then resume at dose
elevation		level-1. If grade 3-4 recurs a 2 nd time, discontinue
(SGOT, SGPT)		sunitinib. Also discontinued if there is no resolution
		to < grade 2 on first episode.
Posterior Reversible	Any occurrence	Cease sunitinib and await recovery with
Encephalopathy Syndrome		symptomatic management. Discontinue treatment.
CPK elevation	Grade 2	Hold sunitinib until ≤ grade 2, then reduce 1 dose level and resume treatment

\* Recurrent grade 3 events require dose reduction.

- Patients requiring a delay of > 4 weeks or > 3 dose reductions should go off protocol therapy but may remain at the principal investigators discretion

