### 8.3.5 Other Hematologic and Non-hematologic Adverse Events (not specifically addressed above)

**General Management Guidelines** 

General Managem	ent Guidennes
Observation	Action
AE resolves promptly* with supportive care	Maintain dose level

 
Grade 3 or higher (non-haematological) AE related to sunitinib and lasting >5 days that does not resolve to grade 2 or below despite maximum supportive care for ≤ 48 hours.
 
Lower grade but related AEs (e.g., creatinine)
 
	Reduce one dose level
AE does not resolve to grade 2 or below after treating patient at the lowest ( i.e. , 25 mg daily) reduced dose level.	In general, remove patient from study

\*Prompt resolution indicates resolution to grade 2 or below.

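### As printed, the AST/ALT row in 8.3.4 tells sites both to resume and to discontinue when a first grade 3-4 episode settles at grade 2, and the CPK row releases its hold at the grade that triggers it

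*Combined protocol and SAP*

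**What the plan says.** Section 8.3.4 gives dose modifications by event and grade. For AST and/or ALT elevation, grades 1-2 keep the dose. Grades 3-4 carry three instructions in one cell:

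- a hold and release: "Sunitinib held until ≤grade 2,then resume at dose" level -1;
- a stop if grade 3-4 recurs a second time;
- a further stop, introduced by "sunitinib. Also discontinued if there is no resolution" and completed by "to < grade 2 on first episode".

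The CPK row of the same table lists one trigger, grade 2, with the action "Hold sunitinib until $\leq$ grade 2, then reduce 1 dose level and resume treatment". No other CPK grade is listed.

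Two general limits bear on recovery. The notes under the dose-level table in section 8.3 say: "Patients who do not recover from toxic effects as required within 3 weeks will be removed from protocol therapy". The notes under the 8.3.4 table say: "Patients requiring a delay of > 4 weeks or > 3 dose reductions should go off protocol therapy", with discretion for the principal investigator to keep the patient on.

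**The concern.** A hold rule needs release and stop conditions that do not overlap. In the AST/ALT row, release includes grade 2, while escaping the stop rule requires a grade below 2. One patient can therefore satisfy both. In the CPK row, the trigger already satisfies the release.

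The first of these is a liver-safety rule. Section 8.2 says hepatic impairment or failure has been reported with the drug, and section 8.3 names liver enzyme changes among the major dose-limiting effects. Section 5.0 names three centres, and nothing in the text ensures that they would resolve the overlap in the same way.

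There is a secondary statistical consequence. Under section 10.1.2 a patient is response evaluable after at least two cycles and a re-evaluation, with an exception for objective progression before the end of cycle 1. A patient stopped for AST/ALT in the first two cycles under one reading would not be evaluable. The same patient, resumed under the other reading, could be.

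**Working it through.** The plan states no figure on this point, so the check is logical: list every grade and apply each rule as printed.

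**AST/ALT, first grade 3-4 episode.** Resume if grade ≤ 2. Discontinue if grade is not < 2.

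| Settled grade | Resume rule | Stop rule | Result |
|---|---|---|---|
| 0-1 | met | not met | resume |
| 2 | met | met | both apply |
| 3-4 | not met | met | stay on hold, then stop |

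The overlap is at grade 2 only. Episode number does not separate the rules: the final clause is expressly about the first episode, and recurrence has its own sentence.

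**Does another rule settle it?**

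- The tie-break in section 8.3 begins "If a patient experiences several adverse events and there are conflicting recommendations". It covers several events in one patient, not two instructions for one event.
- Section 8.3.5 is limited to events "not specifically addressed above". AST/ALT is addressed above.
- The 3-week note in 8.3 removes patients who have not recovered as required. Which grade counts as recovery is the point in dispute. The 8.3.4 note uses a different limit, more than 4 weeks, and names no grade.
- Section 9.1 schedules AST and ALT on day 1 of each six-week cycle, excluding cycle 1. That fixes no date for judging non-resolution: scheduled tests are 6 weeks apart, longer than either the 3-week or the 4-week limit.

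**CPK.** Trigger: grade 2. Release: grade ≤ 2.

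| Grade at onset | Row triggered | Release met |
|---|---|---|
| 2 | yes | yes, at once |
| 3-4 | not listed | no action given |

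At grade 2 the hold has no length, and the row collapses to a one-level reduction. Reading the trigger as grade 2 or higher would cover grades 3-4 but leave the same fault at grade 2. The fatigue row uses the same release, but its holds are triggered at grades 3 and 4, so trigger and release do not coincide there. Whether CPK at grades 3-4 falls to section 8.3.5 is unclear, because CPK elevation is itself listed above.

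**Effect on the evaluable set.** Sections 11.1 and 11.3 count accrual in response-evaluable patients: 14 in stage 1 plus 14 in stage 2 gives 28. A patient who becomes non-evaluable is followed by further accrual, so the rule can change who is among the 28 without reducing the number.

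**The case against.** The strongest reply is that the AST/ALT conflict rests on one character. If the final clause was meant to read ≤ grade 2, the two sentences are complementary and the conflict disappears. Strict signs do appear where an inclusive limit is stated elsewhere. The trial summary has > 28 days since radiation or surgery, against a minimum of 28 days in 5.1.9. A footnote in 9.1 has < 2 mg of anticoagulant, against up to 2 mg in 5.2.7. Section 5.1.6 admits age > 18 but excludes only < 18. Loose drafting or a lost underline could explain all of these. On the other side, ≤ is preserved in the same cell, and < grade 2 also appears as the resolution standard for ongoing toxicity in 9.2 and 12.4. Neither argument is decisive, so the source file must be checked. The CPK trigger needs the same check, since a lost symbol that excluded grade 2 would remove its overlap.

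A second reply is that the sentences work in sequence: resume at grade 2, then stop later if the episode never falls below 2. This is possible, but the row gives no time point or follow-up test to support it.

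A reader might also infer more than the documents support:

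- That each patient stopped early shrinks the 28-patient set. Accrual is defined in evaluable patients, so the set need not shrink.
- That a reported discontinuation rate is distorted. Section 11.2 lists no such endpoint, and section 1.2 gives only a general toxicity objective.
- That sites will in fact diverge. The text permits this but does not show it.

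**Conclusion.** The point stands as an internal inconsistency in the text as supplied, not as a criticism of a design choice. A first grade 3-4 AST/ALT episode that settles at grade 2 leads to two incompatible actions, and no other section resolves them. The CPK row has a release that is met at onset and gives no action for grades 3-4.

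The size is limited. Only first AST/ALT episodes settling at exactly grade 2, and patients with CPK at grade 2 or above, are touched. The documents give no rate for either, and the number may be small. The sample size and the three-or-more decision rule in section 11.3 are unaffected. The possible statistical effect is on the composition of the evaluable set. It is worth correcting mainly because a safety rule should yield one action. The AST/ALT conclusion assumes that the printed < is what the sponsor wrote.

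**What to change.** First check the comparison symbols in the AST/ALT and CPK rows against the source file. If they stand:

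- reconcile the release and stop sentences in the AST/ALT row so that grade 2 leads to one action, and state when non-resolution is judged;
- reconcile the CPK trigger with its release condition, and state which instruction applies at grades 3-4.

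The clinical team sets the thresholds; this review takes no view on which is right. The cost is a wording change in one table, handled through the amendment process in section 15.3. No change to the design, sample size or analysis is needed.

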#### TREATMENT SCHEMA

This study will be a single arm, open-label, phase II trial of sunitinib in patients with metastatic or locally advanced malignant paraganglioma or pheochromocytoma. Oral sunitinib (50mg) will be administered to all patients daily for the first four weeks of a six-week cycle i.e standard scheduling.

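### The AST/ALT and QTc rows of section 8.3.4 do not give a clear restart dose for patients already reduced, and sections 8.3, 8.3.4 and 8.3.5 disagree on the rules that would settle it

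*Combined protocol and SAP*

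**What the plan says.** Section 8.3 lists four dose levels: 0 is 50 mg, -1 is 37.5 mg, -2 is 25 mg and -3 is 12.5 mg. Treatment starts at level 0: "Oral sunitinib (50mg) will be administered to all patients daily for the first four weeks of a six-week cycle" (Treatment Schema). Two general rules in 8.3 apply to all dose modifications. The first is "No dose escalations are permitted after reductions for confirmed toxicity", with QTc prolongation as the only exception. The second is "Patients requiring more than three dose reductions will be removed from protocol therapy".

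The table in section 8.3.4 has two rows that matter here.

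- **AST/ALT, grade 3-4:** "Sunitinib held until ≤grade 2,then resume at dose", continuing on the next line "level-1. If grade 3-4 recurs a 2" (second time), after which sunitinib is discontinued.
- **QTc of 550 msec or more, sunitinib possibly contributing:** "Reduce 2 dose levels and restart sunitinib". The dose then goes up one level after 14 days below 500 msec, and after a further 14 days the original "dose of sunitinib may be resumed".

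The grade 4 haematology rows in 8.3.3 and the fatigue, hand-foot and CPK rows in 8.3.4 word a reduction relatively, as one level down.

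A note below the 8.3.4 table says that patients with more than three "dose reductions should go off protocol therapy but may remain at the principal investigators discretion". Section 8.3.5 gives 25 mg daily as the lowest reduced level.

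**The concern.** A ladder with three steps below the starting dose expects some patients to be on a reduced dose when a new toxicity occurs. Both rows work for a patient at 50 mg. For a patient already reduced, the AST/ALT row can be read in two ways that give different doses, and the QTc row can call for a level that is not in the table. The general rules that might settle these cases are themselves stated inconsistently.

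What is at stake is patient safety and consistent dosing. Section 8.2 notes reports of hepatic impairment and failure with sunitinib, and the QTc row deals with intervals of 550 msec or more. Three centres apply the text (section 5.0), and two of them could restart the same patient at different doses while each believes it is following the protocol.

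**Working it through.** No sample-size or power figure is involved. The check takes each possible dose at onset and applies the rows to the section 8.3 ladder (0, -1, -2, -3 = 50, 37.5, 25, 12.5 mg).

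| Dose at onset (level) | AST/ALT, named level -1 (change) | AST/ALT, one level below current | QTc, two levels down |
|---|---|---|---|
| 50 mg (0) | 37.5 mg (-12.5) | 37.5 mg | 25 mg |
| 37.5 mg (-1) | 37.5 mg (0) | 25 mg | 12.5 mg |
| 25 mg (-2) | 37.5 mg (+12.5) | 12.5 mg | none (would be -4) |
| 12.5 mg (-3) | 37.5 mg (+25) | none (would be -4) | none (would be -5) |

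**AST/ALT.** On the named-level reading, the dose falls from only one of the four levels. From 25 and 12.5 mg the row contradicts the no-escalation rule. From 37.5 mg that rule gives no help, because an unchanged dose is not an escalation. On the relative reading the dose falls from 50, 37.5 and 25 mg, and only 12.5 mg lacks a target. The tie-break in 8.3 chooses between conflicting recommendations when several adverse events coincide; it does not say what one row means.

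**QTc and the limit of three reductions.** Whether the removal rule closes the gap depends on how a two-level cut is counted. Suppose the earlier reductions were single steps:

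- At 25 mg, counting levels: 2 + 2 = 4, more than three, so the patient is removed.
- At 25 mg, counting events: 2 + 1 = 3, not more than three, so the patient stays on with no dose to restart at.
- At 12.5 mg: 3 + 2 = 5 levels or 3 + 1 = 4 events, so the patient is removed on either count.

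Section 8.3 does not say which count applies.

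**Removal rule.** Section 8.3 makes removal mandatory after more than three reductions. The note in 8.3.4 lets such patients remain at the principal investigator's discretion. Where removal would have closed the gap, this reopens it.

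**Lowest level.** If 25 mg is the floor, as 8.3.5 has it, the QTc cut from 37.5 mg (to level -3) also has no target, and neither does the relative AST/ALT step from 25 mg.

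**Original dose.** Take a patient at 37.5 mg after an earlier, unrelated toxicity. The QTc path is 37.5 to 12.5 mg, then 25 mg, then the original dose. That could be 37.5 mg (the dose before the QTc event) or 50 mg (the dose at study start). The QTc exception to the no-escalation rule does not say which.

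**The case against.** The strongest reply is that the AST/ALT row may mean no more than one level below current. It is printed without a space before -1 and is loosely drafted, so its contrast with the other rows is weak evidence of a deliberate fixed dose. This stands as a fair alternative reading. It does not remove the point: the label is defined in section 8.3, a site can reasonably follow it, and the two readings give 37.5 or 25 mg for the same patient at 37.5 mg.

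A reader might infer that the protocol instructs sites to raise the dose after hepatotoxicity, by 50% from 25 mg (37.5/25) or by 200% from 12.5 mg (37.5/12.5). The documents do not support that. Section 8.3 bars escalation after a reduction for confirmed toxicity, so these cases are a row contradicting a rule.

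A reader might also take the recurrence wording to allow a third hepatic episode before discontinuation. The row's next sentence speaks of a first episode, so the natural meaning is the second episode.

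On QTc, the removal rule normally covers 12.5 mg, and three levels below 50 mg alongside three permitted reductions suggests that levels are counted. That is an inference; the count is not stated, and the discretion in 8.3.4 weakens the rule. Sections 8.1.3 and 16.7 say that QTc prolongation has not been seen in clinical trials of sunitinib, which makes the case at 25 mg remote. That bears on how often it would arise, not on whether the text is clear.

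Finally, it is tempting to say that toxicity by dose level could not be compared across centres. Section 11 plans no such comparison.

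**Conclusion.** The point holds as an inconsistency in wording that bears on safety.

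- The AST/ALT restart is ambiguous for every patient below 50 mg. On the named-level reading it gives an unreduced restart at 37.5 mg and conflicts with the no-escalation rule at 25 and 12.5 mg. On the relative reading only 12.5 mg lacks a target.
- The two-level QTc cut has no target from two of the four levels. The clear gap is at 25 mg, where the two ways of counting reductions lead to opposite outcomes.
- The removal rule, the lowest dose level and the original dose in the QTc row also need to be reconciled or defined.

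This rests on the section 8.3 ladder and, for the counting, on the assumption that earlier reductions were single steps. The documents do not say how many patients would be on a reduced dose when either event occurs. With up to 28 response-evaluable patients planned, the number is probably small. No effect on the primary endpoint or on any planned analysis is shown. The gain from a correction is patient safety and consistent dosing across centres.

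**What to change.** Reconcile sections 8.3, 8.3.4 and 8.3.5 in the next amendment so that:

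1. the AST/ALT row gives one unambiguous restart for each of the four dose levels at onset, consistent with the no-escalation rule;
2. the lowest dose level is the same throughout;
3. the QTc row, and the AST/ALT row where it applies, say what happens when the required lower level does not exist;
4. section 8.3 says whether a two-level cut counts as one reduction or two;
5. removal after more than three reductions is either mandatory or discretionary in both places;
6. the original dose in the QTc row is defined for a patient already reduced for another toxicity.

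The doses and clinical rules are for the sponsor to set. The cost is a wording change in these sections, with the usual amendment review. Sample size, endpoints and visit schedule are unaffected.

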### Weekly, Cycle 1, then every 2 weeks, cycle 2+

• Blood pressure and heart rate (by nurse or home monitor)

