### 8.3.1 Non-Hematologic Adverse Events Related to Sunitinib

### Hypertension Management

Specific guidelines for management of this adverse event are provided in the table below. In addition, guidance on the collection and recording of BP information is provided in Appendix VII.

BP measurements – systolic/diastolic Patients not receiving maxima	Treatment/Dose Modification  I antihypertensive therapy:
140-149 mmHg (systolic) OR 90-99 mmHg (diastolic)	
 
Add new or additional antihypertensive meds or increase dose of existing meds
 
Maintain dose of sunitinib
 

150-179 mmHg (systolic) OR	Add new or additional antihypertensive meds or increase dose of existing meds

100-104 mmHg (diastolic)	
 
Hold sunitinib until BP falls to <140/90
 
Decrease sunitinib by 1 dose level if 2 new antihypertensive drugs added to control BP
 
	
≥ 180 mmHg (systolic)  OR  ≥ 105 mmHg (diastolic)	
 
Hold sunitinib until BP controlled
 
Add new or additional antihypertensive meds or increase dose of existing meds
 
Monitor patient closely for hypotension (if on antihypertensive meds) until sunitinib is restarted.
 
Resume sunitinib at the next lower dose level when BP falls to <140/90
 
	
Hypertensive Crisis	

Discontinue sunitinib; Take off study

Hospitalize patient for management

	
modification of antihypertensiv	tihypertensive therapy (four antihypertensives for 2 weeks without dose ve medications): diuretics, beta blocker or central sympathetic blocker, sodilator or calcium channel blocker (CCB)	
> 160 mmHg (systolic) OR > 105 mmHg (diastolic)	
 
Hold sunitinib
 
Maintain antihypertensive meds and monitor patient closely for hypotension until sunitinib is restarted.
 
Resume treatment at one lower dose level when BP falls to <140/90
 
	
Hypertensive Crisis	

Discontinue sunitinib; Take off study

Hospitalize patient for management

	
* Maximal antihypertensive weeks.	therapy is defined as four antihypertensive medications given for 2	

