### 8.3.2Management of Paroxysmal Hypertension

All patients must have adequate blood pressure control before entry into the trial. This includes persistent hypertension as well as episodic paroxysmal hypertension. If the patient experiences paroxysmal hypertension or symptoms thereof during the trial, the patient will cease sunitinib until blood pressure is controlled. The investigators will then ensure that the patient has not progressed. Subsequently, management will be as follows;

1) Gradual titration with a calcium entry blocker (Norvasc) (amlodipine) starting with 5 mg/day for a total of 20 mg/day. The aim will be to keep BP at less than 150/90 mm.

If the above alone is insufficient at maximal doses, consideration will be given to the addition of one of the following agents:

- 2) The mixed alpha/beta receptor blocker labetolol at 200 mg twice daily up to a maximum of 400 mg twice daily.
- 3) The alpha 1 receptor blocker doxazosin (Prazosin) 2 mg up to a maximum of 16 mg/day will be considered for refractory cases.

Should the patient's blood pressure fail to be controlled by these measures, or whose overall condition deteriorates due to uncontrolled hypertension will be discontinued from the protocol and treated with ongoing best supportive care.

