- 24-48 hrs are suggested as elapse time between decision steps suggested in the algorithm unless persistent severe hypertension occurred.
- Hypertension should be graded according to NCI CTCAE Version 3.0 and recorded on CRFs.
- While patients are receiving treatment with sunitinib, the early initiation of antihypertensive treatment for grade 1 or 2 hypertension to minimize more severe or persistent hypertension is not considered a grade 3 adverse event.
- Decisions to hold or decrease the sunitinib dose during treatment must be based on BP readings taken in the clinic by a medical professional.

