### 9.0 EVALUATION DURING AND AFTER PROTOCOL TREATMENT

### 9.1 Evaluation During Protocol Treatment

Investigation	Timing	Investigation	Timing
History and Physical Exam	Day 1 each cycle 	CBC, differential	Day 1 each cycle (prior to treatment) 
Weight, performance status 	Day 1  , 15, and 29 each cycle	PT/INR/PTT 	Twice weekly for first 3 weeks, then as clinically indicated
Clinical tumour measurements	End of every even numbered cycles	Biochemistry	Day 1 each cycle 
Blood pressure, heart rate 	Weekly for cycle 1  then Day 1  , 15, and 29 each cycle thereafter (assessed by nurse or home monitor)	BUN, serum creatinine/clearance  , sodium, potassium, chloride, bicarbonate, bilirubin, alkaline phosphatase, AST, ALT, LDH, total protein, calcium, phosphate, albumin, glucose, CPK	Day 1 each cycle 
Adverse Events/ Toxicity Evaluation 	Each visit at the end of every cycle	Amylase, Lipase	Day 1 each cycle 
Urinalysis	Day 1 each cycle 	TSH, T4	Day 1 each cycle 
EKG	Day 1 of even numbered cycles 	LVEF  / MUGA	Day 1 of even numbered cycles 
Endocrine testing (urinary metanephrines, catecholamines and serum chromogranin A)	Day 1, every 2 cycles 	CXR or CT 	End of even numbered cycles

Each visit:

 $^{1}$  Repeat daily if BP > 150/100 mmHg if previously WNL, OR recurrent, persistent (> 24Hrs) or symptomatic increase by > 20 mmHg and manage as per Section 8.3.

<sup>2 Only for patients receiving low dose anticoagulants (< 2 mg coumadin, warfarin) or LMW heparin.

 $^{3}$  Only required if serum creatinine is > ULN. Creatinine clearance to be measured directly by 24 hour urine sampling or as calculated by Cockcroft Formula: GFR = 1.04 x (140-age) x weight in kg NB: this version of the formula incorporates a 15% reduction for women

<sup>4 To ensure comparability, baseline xrays/scans/LVEF and subsequent xrays/scans/LVEF to assess response and cardiac effects must be performed using identical techniques.

<sup>5 Adverse events will be recorded and graded using NCI Common Terminology Criteria for Adverse Events Version 3.0 (CTCAE) (Appendix IV)

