<sup>6 LVEF required in patients with class II NYHA, prior anthracyclines or prior central thoracic radiation, and at investigator's discretion in patients without cardiac risk factors. Identical technique must be used throughout.

<sup>7 Excluding cycle 1

<sup>8 Can be once per cycle at physician's discretion for cycle 3+

<sup>9 Weekly for cycle 1 then day 1, 15, 29 for cycle 2-3, then can be once per cycle at physician's discretion. Repeat daily if BP > 150/100mm HG if previously within normal limits, or recurrent, persistent (>24 hrs) or symptomatic increase > 20 mm Hg and manage as per protocol. Measurements may be performed more frequently at physician's discretion.

<sup>10 Measurements do not have to be repeated cycle 1 Day 1, if screening visit occurred  $\leq$  3 days prior.

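### Section 8.3.4 allows sunitinib holds only on clinic blood pressure readings, while 8.3.2 stops the drug for a paroxysm or its symptoms; no precedence is stated and a high home reading has no stated route to a clinic reading

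*Combined protocol and SAP*

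**What the plan says.** Evidence for a dose decision. Section 8.3.4, in the bullets that precede the LVEF rules: "Decisions to hold or decrease the sunitinib dose during treatment must be based on BP readings taken in the clinic by a medical professional".

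Paroxysms. Section 8.3.2: "If the patient experiences paroxysmal hypertension or symptoms thereof during the trial, the patient will cease sunitinib until blood pressure is controlled". No setting, observer or numeric threshold is attached to this trigger.

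Hold bands. The hypertension table in 8.3.1 calls for a hold at 150-179 systolic or 100-104 diastolic, and again from 180 or 105, where the instruction is "Hold sunitinib until BP controlled". Patients on maximal antihypertensive therapy have a separate hold row. Hypertensive crisis leads to permanent discontinuation. None of these rows says where the pressure is measured.

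Who takes the scheduled reading. The Trial Summary and the table in 9.1 both allow a nurse or a home device ("assessed by nurse or home monitor"), and Appendix VII (1.2) provides for a patient blood pressure diary.

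How often. Note 9 to 9.1: "Weekly for cycle 1 then day 1, 15, 29 for cycle 2-3, then can be once per cycle at physician's discretion". Note 8, on weight and performance status: "Can be once per cycle at physician's discretion for cycle 3" and later. Section 8.2 and Appendix VII (1.1) set a minimum of one blood pressure reading every two weeks, and Appendix VII applies it to the whole of treatment.

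**The concern.** Two mandatory rules give different answers for the same patient. Someone at home with symptoms of a paroxysm must stop under 8.3.2. Under 8.3.4, that stop is not properly based until a clinic reading supports it. Someone whose home device shows a value in an 8.3.1 hold band is in a similar position: the value comes from an accepted scheduled assessment, yet it cannot itself support the hold, and nothing says a clinic reading must follow.

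Hypertension is one of the dose-limiting effects named in 8.3, and section 2.0 notes that these tumours may secrete catecholamines. The stake is mainly patient safety. There is a secondary effect on objective 1.2 (toxicity): the three centres in 5.0 could each follow the text and still record different holds and reductions for the same event.

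**Working it through.** The plan gives no statistical figure on this point. The check is a comparison of sections plus simple calendar arithmetic.

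**What each rule needs**

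| Section | What starts the action | Action | Clinic reading required? |
|---|---|---|---|
| 8.3.4 bullets | Clinic reading only | Hold or decrease | Yes, no exception given |
| 8.3.2 | Paroxysm or its symptoms | Stop until controlled | Not asked for |
| 8.3.1 bands | Pressure in a band | Hold, in some rows with a reduction | Not stated |
| 8.3.1 crisis row | Hypertensive crisis | Discontinue | Not stated; neither a hold nor a decrease |
| 8.2 | Above 150/100 if previously normal, or a recurrent persistent rise of more than 20 mmHg | Repeat daily | Place and observer not stated |

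A stop until pressure is controlled is a hold, so 8.3.2 falls within the subject matter of the 8.3.4 bullet. The trigger in 8.3.2 can be met by symptoms alone; the bullet in 8.3.4 cannot. No section ranks one above the other.

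For home readings, the chain is incomplete. Detection is covered (9.1), and so is repetition (8.2). The step from a repeated high home value to a clinic measurement is written nowhere. Section 8.3.2 itself describes this hypertension as episodic, so a later clinic value may be normal and the 8.3.4 condition would still be unmet.

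**What the schedule guarantees in later cycles**

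Inputs: a 6-week cycle with 4 weeks of dosing (8.1); physical examination on Day 1 of each cycle; Day 1 assessments allowed up to 7 days early (9.1, note 11).

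- Cycle length: 6 × 7 = 42 days. Dosing: 4 × 7 = 28 days (days 1-28).
- The next Day 1 is day 43, which is 43 − 28 = 15 days after the last dose. At the early edge of the window it is day 36, or 36 − 28 = 8 days after.
- Interval between consecutive Day 1 assessments: nominally 42 days, and up to 42 + 7 = 49 if the first is early and the next on time, assuming no cycle delay.
- Dosing days after Day 1: 28 − 1 = 27.

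Those 27 days contain no scheduled clinic reading if three conditions hold together: cycle 3 or later; the physician uses note 8 to drop the Day 15 and 29 weight and performance status checks; and blood pressure is taken by home monitor. After cycle 3, note 9 lets the Day 15 and 29 pressure readings be dropped as well.

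In cycles 1 and 2 the Day 15 and 29 weight and performance status checks have no such option, and Day 15 is a dosing day. Appendix VII (3.1) asks for current pressure at every clinic visit. If the Day 15 check is done in clinic (9.1 does not say), it supplies a qualifying reading.

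**Frequency**

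The two-weekly minimum implies 42 / 14 = 3 readings per cycle. Note 9 permits 1. The same note is repeated in Appendix I (note 5), so both versions are current text.

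**The case against.** The strongest defence is that the sections fit together. Section 8.3.1 gives bands without a setting, and the 8.3.4 bullet supplies the setting. The neighbouring bullet speaks of an algorithm and of persistent severe hypertension, so the list reads like notes to the hypertension table. Surveillance at home with confirmation in clinic is a coherent design. Section 8.3.2 is the specific provision for paroxysms and can be read as standing alone.

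Much of this stands. Read that way, 8.3.1 and 8.3.4 do not conflict, and accepting home readings for surveillance does not by itself contradict a clinic-only rule for dose decisions. Two gaps remain. The bullet's wording is unrestricted and it is printed in 8.3.4, so the exemption of 8.3.2 is an inference that the text does not state. Also, confirmation in clinic is nowhere required. The rule in 8.3 for conflicting recommendations does not help: it selects among dose adjustments when a patient has several adverse events and does not say what evidence starts a hold.

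A reader might infer more: that dangerous readings on drug cannot trigger a hold at all. The documents do not support this. A clinic reading, including an unscheduled one, can always support a hold. Daily repeats are required above 150/100 in previously normal patients, and more frequent measurement is allowed. Hypertensive crisis leads to discontinuation, which the 8.3.4 wording does not cover. Nor do the documents say that paroxysms usually occur outside the clinic.

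**Conclusion.** The conflict between 8.3.4 and 8.3.2 is real, and the route from a home reading to a dose decision is incomplete. Under literal compliance a hold may be delayed or missed, or centres may handle the same event differently. The documents do not show that a hold is impossible.

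On size, the 27 dosing days without a scheduled clinic reading are a worst case that needs all three conditions above. A reader might state this as 0 of 28 dosing days covered. That is right only if the Day 1 assessment is treated as off-drug; a clinic reading on Day 1 itself makes it 1 of 28. The documents give no basis for estimating how often the worst case would arise.

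The once-per-cycle option in 9.1 and Appendix I also contradicts the two-weekly minimum in 8.2 and Appendix VII (1 against 3 readings per cycle). The primary endpoint, sample size and error rates are unaffected. The point merits correction because two mandatory stopping rules disagree on a named dose-limiting toxicity and the repair is cheap.

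**What to change.** Reconcile the 8.3.4 bullet with 8.3.2, 8.3.1 and the home-monitoring provisions in the Trial Summary and 9.1. State in one place:

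- whether a home reading, or symptoms without a reading, can start a hold;
- how a clinic reading follows a high home reading;
- which section prevails for paroxysms.

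Separately, reconcile note 9 of 9.1 and note 5 of Appendix I with section 8.2 and Appendix VII on how often pressure is measured. Which rule and which frequency to adopt are clinical choices for the sponsor.

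The source of each reading (clinic or home) should be recorded with any hypertension-driven hold or reduction, so that these events can be interpreted under objective 1.2. The case report forms are not in the documents, so this may already be captured.

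The cost is amendment wording and, if needed, one data field. No statistical element of the plan changes.
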